## **10.5 Multiple Comparisons, Multiplicity**

To control family-wise error rate, statistical hypothesis testing for the primary endpoint will be hierarchically dose ordered, testing first the 200mg dose versus placebo at 0.05 2-sided; then followed by the 100mg dose versus placebo at 0.05 2-sided if the 200mg dose reaches  $p \leq 0.05$ ; and finally, the 50mg dose versus placebo at 0.05 2-sided if the 100mg dose reaches  $p \leq 0.05$ .

Secondary and exploratory endpoints will not be subject to alpha control, rather these endpoints will be interpreted nominally at the 2-sided 5% level.

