### 13.3.2 Dose Response Statistical Hypothesis

For the Primary Efficacy Analysis, the null hypothesis is that there is no difference in the profile of log A4 change from baseline through 12 weeks of blinded randomized treatment between tildacerfont and placebo. The alternative hypothesis is that there is difference in the profile of log A4 change from baseline through 12 weeks of blinded randomized treatment between tildacerfont and placebo.

To assess this dose response hypothesis, repeated measures random coefficients mixed-effects model will be used:

$$y_{ijt} = (\beta_0 + \xi_i) + (\beta_1 + \eta_i)t + (\beta_2 + \theta_i)t^2 + \beta_{4j}I_j + \beta_{5j}I_jt + \beta_{6j}I_jt^2 + \beta_7\kappa + \beta_8G + \beta_9D + e_{ijt}$$

where:

$y_{ijt}$  is the log A4 change from baseline value for subject  $i$ ,  $i = 1, \dots, N$ , at time  $t$  in treatment group  $j$ ,  $j = 1, 2, 3, 4$  (1 = 200mg tildacerfont, 2 = 100mg tildacerfont, 3 = 50mg tildacerfont and 4 = placebo),  $I_t$  is the indicator for randomised treatment ( $I_t = 1$  for tildacerfont 200mg,  $=2$  for 100mg,  $=3$  for 50mg and  $=4$  for placebo),  $\kappa$  is log baseline A4 value,  $G$  is the indicator for sex ( $G = 1$  male,  $G = 0$  female) and  $D$  baseline GC dose (in HCe),

$\beta_0$  is the fixed intercept effect.

$\beta_1$  is the fixed effect of the linear component of time

$\beta_2$  is the fixed effect of the quadratic component of time

$\beta_{4j}$  is the fixed effect of treatment  $j$  parametrized such with  $\beta_{44} = 0$

$\beta_{5j}$  is the effect of treatment  $j$  on the linear component of time parametrized such that  $\beta_{54} = 0$

$\beta_{6j}$  is the effect of treatment  $j$  on the quadratic component of time parametrized such that  $\beta_{64} = 0$

$\beta_7$  is the fixed effect of baseline log A4

$\beta_8$  is the fixed effect of gender

$\beta_9$  is the fixed effect of baseline GC dose

$\xi_i$  is the random effect of subject  $i$  on the intercept

$\eta_i$  is the random effect of subject  $i$  on the linear component of time

$\theta_i$  is the random effect of subject  $i$  on the quadratic component of time

$e_{ijt}$  is the random error for subject  $i$  on treatment  $j$  and time  $t$ .

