The random effects,  $\xi_i$ ,  $\eta_i$ , and  $\theta_i$  are assumed independent and identically normally distributed with variance components  $\sigma_\xi^2$ ,  $\sigma_\eta^2$ , and  $\sigma_\theta^2$ , and, independently, the random error  $e_{ij}$  is normally distributed with variance  $\sigma^2$ .

The dose response Primary Efficacy Analysis therefore corresponds to the formal hypothesis statement,

$H_{0L}: \beta_{51} = \beta_{52} = \beta_{53} = 0$  vs  $H_{1L}: \beta_{5j} \neq 0$  for at least one  $j$

and

$H_{0Q}: \beta_{61} = \beta_{62} = \beta_{63} = 0$  vs  $H_{1Q}: \beta_{6j} \neq 0$  for at least one  $j$

The union intersection hypothesis  $H_{0L} \cap H_{0Q}$  represents the null that there is no dose response for tildacerfont versus placebo.

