### 13.3.3 Dose Response Modeling and Testing

Statistical testing for dose response will be performed using the repeated measures random coefficients mixed-effects model described in [Section 13.3.2](#). A4 values will be log transformed prior to analysis. The model will comprise of the log A4 change from baseline through to study Week 18, i.e. though 12 weeks of double blind randomized treatment; note the actual time, in days, from baseline to each post baseline A4 value through to study week 18 will be used in this analysis. Randomized treatment group and sex will be included in the model as class factors and baseline GC dose (in HCe) as continuous covariate. Subject specific intercept, time (in days)

and time x time random effects will be included. Further, randomized treatment by time and randomized treatment by time x time interactions will be included. The model will be fitted using maximum likelihood estimation. If the variance component for time or time x time are estimated to be zero then the corresponding term (or terms) will be retained in the model as fixed effects and the analysis re-run.

To test the union intersection hypothesis  $H_{0L} \cap H_{QL}$ , the model will be fitted with and without the randomized treatment by time and randomized treatment by time squared interactions terms. The difference in -2 log likelihood between models will be compared to the  $\chi^2_{df}$  cumulative distribution function on the appropriate degrees of freedom (i.e.  $df = 6$ ), this will provide the p-value to determine if the union intersection hypothesis can be rejected at the 10% alpha level; if so then there is evidence for a treatment effect of tildercerfont over placebo.

The fitted A4 change from baseline versus time profile will be extracted from the model for each randomized treatment and displayed graphically, superimposed upon the A4 time profiles for individual subjects.

Note, the programming of the repeated measures random coefficients mixed-effects model is particularly complex, hence example SAS codes perform the analysis are presented in Appendix D.

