LBASE=LOG (BASE) ;
LCFB=LPULSE-LBASE;
RUN;
DATA STUDY2;
  SET STUDY2;
  G=EXERTYPE;
RUN;

PROC SORT DATA=STUDY2;
  BY ID TIME;
RUN;

** FULL MODEL WITH TIME*G AND TIME*TIME*G = DOSE RESPONSE PARAMETERS **;

PROC MIXED DATA=STUDY2 COVTEST NOCLPRINT METHOD=ML ;
  CLASS ID G ;
  MODEL PULSE = BASE TIME G TIME*G TIME*TIME TIME*TIME*G /
  SOLUTION OUTP=PRED1RX OUTPM = PRED1FX;
  RANDOM INTERCEPT TIME TIME*TIME / SUBJECT = ID SOLUTION;

  ** ESTIMATES WHEN BASELINE = 90 BPM, I.E. LOG BASE = 4.5 **;
ESTIMATE "INTERCEPT: 1 " INTERCEPT 1 BASE 90 G 1 0 0 ;
ESTIMATE "INTERCEPT: 2 " INTERCEPT 1 BASE 90 G 0 1 0 ;
ESTIMATE "INTERCEPT: 3 " INTERCEPT 1 BASE 90 G 0 0 1 ;

  ** TRT EFFECTS AND CONTRASTSAT 600 DAYS **;

ESTIMATE "VALUE AT 600 1" INTERCEPT 1 BASE 90 G 1 0 0 TIME 600 G*TIME 600 0 0
TIME*TIME 360000 G*TIME*TIME 360000 0 0 ;
ESTIMATE "VALUE AT 600 2" INTERCEPT 1 BASE 90 G 0 1 0 TIME 600 G*TIME 0 600 0
TIME*TIME 360000 G*TIME*TIME 0 360000 0 ;
ESTIMATE "VALUE AT 600 3" INTERCEPT 1 BASE 90 G 0 0 1 TIME 600 G*TIME 0 0 600
TIME*TIME 360000 G*TIME*TIME 0 0 0 ;
ESTIMATE "VALUE AT 600 1-3" G 1 0 -1 TIME 0 G*TIME 600 0 -600 TIME*TIME 0 G*TIME*TIME 360000 0 0;
ESTIMATE "VALUE AT 600 2-3" G 0 1 -1 TIME 0 G*TIME 0 600 -600 TIME*TIME 0 G*TIME*TIME 0 360000 0 ;
ESTIMATE "LINEAR CONTRAST @ 600" G -1 0 1 TIME 0 G*TIME -600 0 600
TIME*TIME 0 G*TIME*TIME -360000 0 0;
ESTIMATE "QUADRATIC CONTRAST @ 600" G 1 -2 1 TIME 0 G*TIME 600 -1200 600
TIME*TIME 0 G*TIME*TIME 360000 -720000 0;
ODS OUTPUT FITSTATISTICS=FIT1;
ODS OUTPUT SOLUTIONF=F1;
ODS OUTPUT COVPARMS =C1;

TITLE 'RC MODEL TIME G TIME*G TIME*TIME TIME*TIME*G';
RUN;
TITLE;

** REDUCED MODEL WITH TIME*G AND TIME*TIME*G = DOSE RESPONSE PARAMETERS **;
PROC MIXED DATA=STUDY2 COVTEST NOCLPRINT METHOD=ML ;
  CLASS ID G ;
  MODEL PULSE = BASE TIME G TIME*TIME /
  SOLUTION;
  RANDOM INTERCEPT TIME TIME*TIME / SUBJECT = ID SOLUTION;

  ** ESTIMATES WHEN BASELINE = 90 BPM, I.E. LOG BASE = 4.5 **;
ESTIMATE "INTERCEPT: 1 " INTERCEPT 1 BASE 90 G 1 0 0 ;
ESTIMATE "INTERCEPT: 2 " INTERCEPT 1 BASE 90 G 0 1 0 ;
ESTIMATE "INTERCEPT: 3 " INTERCEPT 1 BASE 90 G 0 0 1 ;

  ** TRT EFFECTS AND CONTRASTSAT 600 DAYS **;
```

```
ESTIMATE "VALUE AT 600 1" INTERCEPT 1 BASE 90   G   1 0 0   TIME  600 TIME*TIME  360000  ;
ESTIMATE "VALUE AT 600 2" INTERCEPT 1 BASE 90   G   0 1 0   TIME  600 TIME*TIME  360000  ;
ESTIMATE "VALUE AT 600 3" INTERCEPT 1 BASE 90   G   0 0 1   TIME  600 TIME*TIME  360000  ;

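### The SAP 13.3.3 global test sees only non-parallel A4 profiles over treatment Weeks 4 to 12, not the whole profile difference worded in 13.3.2, and it is not reconciled with the dose-ordered 5% testing in 10.5

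*SAP*

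**What the plan says.** **The null.** SAP 13.3.2 states that "the null hypothesis is that there is no difference in the profile of log A4 change from baseline through 12 weeks" of blinded treatment between tildacerfont and placebo. It then formalises this as two sets of restrictions, β51 = β52 = β53 = 0 (linear) and β61 = β62 = β63 = 0 (quadratic), whose intersection "represents the null that there is no dose response for tildacerfont versus placebo". The treatment terms β4j are not restricted.

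**The test.** In SAP 13.3.3, "the model will be fitted with and without the randomized treatment by time and randomized treatment by time squared interactions terms", and the change in -2 log likelihood is referred to a chi-square on 6 df. The null can be "rejected at the 10% alpha level; if so then there is evidence for a treatment effect of tildercerfont over placebo". Only post-baseline values enter. The Appendix D example likewise drops the time-zero rows, and its reduced model keeps treatment: "MODEL PULSE = BASE TIME G TIME*TIME".

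**The other primary rule.** In SAP 10.5, "statistical hypothesis testing for the primary endpoint will be hierarchically dose ordered, testing first the 200mg dose versus placebo at 0.05 2-sided", then 100 mg, then 50 mg. That section names no model, time point or contrast and does not mention the 6-df test; 13.3.3 does not mention the dose sequence. It adds that "Secondary and exploratory endpoints will not be subject to alpha control".

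**Where dose-versus-placebo p-values for A4 are defined.** Only in 13.4.1, the first secondary analysis, and its supportive MMRM (13.4.1.1). Yet 13.3.5.1 expects the primary method to yield a treatment effect with a CI, and 13.3.5.3 expects Week 18 effects by dose. A 6-df chi-square gives neither.

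**The concern.** There are two separate problems.

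1. The worded null concerns the whole profile; the test concerns only its shape. Because β4j is free in both models and no baseline row ties the arms together at time zero, β4j acts as a vertical shift per arm. Any part of the drug effect that is constant over treatment Weeks 4, 8 and 12 is absorbed and cannot contribute to rejection. Non-rejection is therefore not evidence of no effect. The same test is carried over to 17-OHP (13.4.3) and ACTH (13.5.8).

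2. A reader cannot tell which result makes the primary analysis positive: the global test at 10%, the dose sequence at 5%, or both. SAP Section 4 settles conflicts between SAP and protocol, and SAP 9.2 sets 0.05 unless otherwise noted, but neither settles a conflict inside the SAP.

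**Working it through.** **Reproducing the plan's figures.** Three linear plus three quadratic interaction terms give df = 6, as stated. Restricting the three β4j as well gives 9. Sample size: 15/(1 - 0.15) = 17.6, so 18 per group and 72 in total, as stated. A two-group comparison with n = 15, difference 50 and SD 30 has power 0.995, so at least 80% is true as a lower bound for that comparison.

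**Assumptions for power** (the documents give no log-scale SD or within-subject correlation). Treatment Week 12 reductions of 50/41/29/0% for 200/100/50 mg/placebo; compound symmetry with SD σ and correlation ρ of 0.3 to 0.8; complete data; 18 per arm. If post/baseline ratios are lognormal, the planned 30% SD corresponds to σ = √ln(1 + 0.3²) = 0.29 with no mean change and √ln(1 + 0.6²) = 0.55 at a 50% reduction. I therefore take σ = 0.3 and 0.5, with 0.7 as a pessimistic check.

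**Formulas.** Let f be the fraction of the Week 12 log effect present at treatment Weeks 4, 8 and 12, and S the sum of squared deviations of the arm effects from their mean. The log effects are -0.693, -0.528, -0.342 and 0, so S = 0.265. Then

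- 6-df noncentrality = n S Σ(f - f̄)² / [σ²(1 - ρ)]
- 9-df noncentrality = the above + 3 n S f̄² / [σ²(1 + 2ρ)]

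If f is constant, the first is zero whatever σ, ρ or the effect size, so power equals alpha. Worked case, linear onset (f = 1/3, 2/3, 1), σ = 0.5, ρ = 0.3: 6 df gives 18 × 0.265 × 0.222 / 0.175 = 6.06. The 9-df test adds 18 × 0.265 × 1.333 / 0.40 = 15.9, for 21.97. Against the 10% critical values 10.645 and 14.684, power is 0.54 and 0.96.

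**Onset anchor.** Protocol 2.3.2 reports a 13% A4 reduction at 2 weeks and a maximum mean reduction of 81% over 12 weeks. ln(0.87)/ln(0.19) = 8% of the log effect at 2 weeks, against 2/12 = 17% if linear; that is time to the power 1.38. This is rough: the doses differ, 81% is a maximum, and the studies were small and open-label.

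Power at the 10% level, 18 per arm, over ρ = 0.3 to 0.8:

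| Onset | 6 df, σ 0.3 | 6 df, σ 0.5 | 6 df, σ 0.7 | 9 df, σ 0.5 |
|---|---|---|---|---|
| Constant from Week 4 | 0.10 | 0.10 | 0.10 | 0.96 or more |
| 28-day half-time | 0.61-0.99 | 0.28-0.71 | 0.19-0.44 | 0.97 or more |
| Linear | 0.94-1.00 | 0.54-0.98 | 0.32-0.79 | 0.96 or more |
| Protocol 2.3.2 anchor | 0.99-1.00 | 0.67-1.00 | 0.41-0.91 | 0.96 or more |

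With 15 per arm and σ = 0.5, the linear and anchored rows become 0.47-0.95 and 0.59-0.99, against 0.91 or more for 9 df.

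**Decision rule under no treatment effect**, taking the 200 mg step as the Week 12 contrast. If the two tests were independent, either one succeeds with probability 0.10 + 0.05 - 0.005 = 0.145; simulation with known covariance gives about 0.14. Both succeed with probability about 0.01.

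**Decision rule, power for a 200 mg claim** (σ = 0.5, 18 per arm). Alone: 0.693 / (0.5 × √(2/18)) = 4.16 standard errors, power 0.98. With the 6-df test at 10% as a gate, at ρ = 0.3/0.5/0.8: 0.53/0.68/0.96 for linear onset and 0.67/0.81/0.98 for anchored onset. The loss runs from almost none to 0.98 - 0.53 = 0.45.

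**Appendix D rows.** With treatment as a class variable the design has 13 columns and rank 10. `TIME*TIME` equals the sum of the three `G*TIME*TIME` columns, so a row is estimable only if its three `G*TIME*TIME` coefficients sum to its `TIME*TIME` coefficient. The 1-3 row reads "G*TIME 600 0 -600 TIME*TIME 0 G*TIME*TIME 360000 0 0": 360000 against 0, not estimable. With 360000 0 -360000 it is. The 2-3, linear, quadratic and group-3 value rows fail in the same way.

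**The case against.** The formal hypotheses in 13.3.2 and the test in 13.3.3 agree with each other; only the worded null differs. With time counted from baseline, β4j is an extrapolated time-zero difference, expected near zero under randomisation if onset is smooth, so putting the drug effect in the time terms is coherent, if inefficient. Protocol 2.3.2 and 4.2 describe a response that builds over 12 weeks, which is where the 6-df test works best. All of this stands, and it is why the power loss is put as partial and dependent on assumptions.

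A reader might infer that the primary analysis cannot detect a treatment effect. That holds only for a gap already constant at treatment Week 4, which is not the onset the documents suggest. A reader might also infer that rejection is invalid. It is not: under randomisation, non-parallel profiles are evidence of some effect, though without direction.

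A reader might take 0.14 as the trial's false-positive rate. No section permits claiming success on whichever test succeeds, and 10.5 gives family-wise control as its purpose. The figure shows only what the silence would allow.

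Finally, 13.4.1 calls the dose contrasts part of the dose-response modelling, so 10.5 can be read as governing them. But 13.4.1 labels them secondary and 10.5 makes secondary endpoints nominal, so that reading has to be written down. Appendix D is example code on unrelated three-group data, so its rows are a lesser matter.

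**Conclusion.** Both parts hold and need correcting before unblinding.

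The 6-df test does not test the worded null. The zero noncentrality for a constant gap is algebra and needs no assumption. The partial loss under gradual onset rests on the assumed σ, ρ, reductions and compound symmetry, which is simpler than the SAP's random-coefficient covariance: material at σ = 0.5 with low correlation, small at σ = 0.3 for linear or anchored onset.

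The decision rule is undefined. The 10% and 5% levels both attach to the primary analysis, no text ranks them, and the contrast for the dose steps is unnamed. An early, sustained effect would still be estimated in 13.4.1 and the MMRM, but only nominally.

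**What to change.** 1. In SAP 10.5 and 13.3.3, state one primary decision rule and one alpha, replacing the unreconciled 10%. Name the contrast for the dose steps: the study Week 18 difference in mean log A4 change from baseline, each dose versus placebo, from the full 13.3.3 model. Two options are open. Either make these ordered contrasts the primary tests, with the global test supportive; or keep the global test as a gate and accept the power loss shown above. The ordered sequence needs no gate for error control.
2. Define the global null as β4j = β5j = β6j = 0 and remove `G` as well as both interactions from the reduced model (9 df). Do the same for 17-OHP and ACTH.
3. Balance the `G*TIME*TIME` coefficients in the Appendix D rows (for example 360000 0 -360000) before they are adapted to this trial.
4. Lesser: say in SAP 7 that the 80% figure is for a pairwise percent-change comparison, not for the log-scale likelihood-ratio test.

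**Cost.** Wording and code, with no new data or visits; 13.4.1 already produces the contrasts. Demoting the global test departs from the primary analysis in Protocol 9.4.2 and must be recorded in SAP Section 15. The 9-df test gives up a little if arms are equal at treatment Week 4 and then diverge steadily: at most 0.004 for the reductions above and 0.025 for 30/20/10% (5% level, 15 to 18 per arm, σ 0.3 to 0.7, ρ 0.3 to 0.8).

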### 13.4.1 First Secondary Efficacy Analysis

The First Secondary Efficacy Analysis (see [Table 1](#), Analysis 2.1) relates to the change from baseline in A4 as assessed on the log scale after 12 weeks on double-blind, placebo-controlled treatment. This analysis will be achieved as an integral part of the dose response modelling as described in [Section 13.3.3](#).

The estimated mean change from baseline in log A4 values at 4, 8 and 12 weeks of double blind randomized treatment will be extracted from the model by treatment arm as will the difference and associated 95% CI and p-value between each tildacerfont dose and placebo at each of 4, 8 and 12 weeks. To facilitate ease of interpretation, the estimated mean change from baseline in log A4 for each tildacerfont dose and placebo will be back transformed resulting in the estimated ratio of geometric means to baseline, i.e. the back transformed log scale estimated mean change becomes  $\{\text{estimated A4 geometric mean at time } x\}/\{\text{estimated A4 geometric mean at baseline}\}$  = GMR. Hence, GMR – 1 becomes the percentage CFB in geometric means. Further, the difference between each tildacerfont dose and placebo in estimated mean change from baseline in log A4 (along with the associated 95% CI) will also back transformed resulting in the ratio of  $\{\text{A4 GMR tilda at time } x\}/\{\text{A4 GMR placebo at time } x\}$  as the measure of treatment effect. And, again,  $\{\text{A4 GMR tilda at time } x\}/\{\text{A4 GMR placebo at time } x\} - 1$  becomes the percentage reduction (or increase) in geometric mean A4 values at time  $x$  for tildacerfont compared to placebo.

In addition orthogonal linear and quadratic contrasts between treatments at 12 weeks of double blind randomized treatment will also be estimated as a supportive measure of dose response at this time point.

Example SAS codes in relation to the First Secondary Efficacy Analysis are provided in Appendix D.

A serial plot will be presented of the estimated mean change from baseline in log A4 over time. The y-axis will be the percent CFB (i.e  $100 \{ \exp(\text{estimated change from baseline in log A4}) - 1 \}$ ) and the x-axis will represent the Part A visits, baseline, Week 4, Week 8, and Week 12 of double blind randomized treatment. All treatment groups will be presented on the graph.

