#### **13.4.1.1 Supportive MMRM Analysis**

A supportive analysis of the log change from baseline in A4 will be achieved via conventional MMRM modelling as described in [Section 13.3.5.1](#). The log scale change from baseline (CFB) least squares (LS) means will be extracted from the model for each tildacerfont dose and placebo at study Weeks 10, 14 and 18, along with the associated SEs and 95% CIs. Further, the treatment effect for each tildacerfont dose versus placebo, being the corresponding difference in log scale LS means, will also be extracted along with the associated SE, 95% CI and 2-sided p-values.

To facilitate ease of interpretation, LS means, differences in LS means and associated 95% Cis s will be back transformed in the same fashion described in [Section 13.4.1](#).

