ESTIMATE "VALUE AT 600 1-3" G   1 0 -1 TIME   0   TIME*TIME  0   ;
ESTIMATE "VALUE AT 600 2-3" G   0 1 -1 TIME   0   TIME*TIME  0   ;
ESTIMATE "LINEAR CONTRAST @ 600"      G   -1 0 1 TIME   0   TIME*TIME  0   ;
ESTIMATE "QUADRATIC CONTRAST @ 600"    G   1 -2 1 TIME   0   TIME*TIME  0   ;

ODS OUTPUT FITSTATISTICS=FIT2;
ODS OUTPUT SOLUTIONF=F2;
ODS OUTPUT COVPARMS =C2;

TITLE 'RC MODEL TIME G TIME*TIME';
RUN;
TITLE;

DATA C1;
  SET C1;
  TP='COVPARM';
RUN;
DATA F1;
  SET F1;
  TP='FIXED  ';
RUN;

DATA DF1;
  LENGTH P $24;
  LENGTH MODEL $12;
  SET F1(RENAM=(EFFECT=P) ) C1(RENAM=(COVPARM=P));
  IF ESTIMATE NE 0;
  DUM=1;
  MODEL='FULL';
  KEEP MODEL TP ESTIMATE STDERR P DUM;
RUN;

/*
PROC PRINT DATA = DF1;
RUN;
*/

DATA C2;
  SET C2;
  TP='COVPARM';
RUN;
DATA F2;
  SET F2;
  TP='FIXED  ';
RUN;

DATA DF2;
  LENGTH P $24;
  LENGTH MODEL $12;
  SET F2(RENAM=(EFFECT=P) ) C2(RENAM=(COVPARM=P));
  IF ESTIMATE NE 0;
  DUM=1;
  MODEL='REDUCED';
  KEEP MODEL TP ESTIMATE STDERR P DUM;
RUN;

/*
PROC PRINT DATA = DF2;
RUN;
*/
```

```
DATA DF;
  SET DF1 DF2;
  RUN;

/*
PROC PRINT DATA = DF;
RUN;
*/

PROC SORT DATA = DF;BY MODEL;RUN;
PROC UNIVARIATE DATA = DF NOPRINT;
BY MODEL;
VAR DUM;
OUTPUT OUT=DF_ SUM=DF;
RUN;

/*
PROC PRINT DATA = DF_;
RUN;
*/

PROC TRANSPOSE DATA = DF_ OUT=DFT(DROP=_NAME_ _LABEL_);
VAR DF;
ID MODEL;
RUN;

DATA DFT;
  SET DFT;
  DUM=1;
RUN;

/*
PROC PRINT DATA = DFT;
RUN;
*/

DATA LOGL1;
  SET FIT1(RENAM=(VALUE=NEG2LOGLFULL));
  IF SUBSTR(DESCR,1,2)=' -2';
  DUM=1;
  KEEP DUM NEG2LOGLFULL;
RUN;

DATA LOGL2;
  SET FIT2(RENAM=(VALUE=NEG2LOGLRREDUCED));
  IF SUBSTR(DESCR,1,2)=' -2';
  DUM=1;
  KEEP DUM NEG2LOGLRREDUCED;
RUN;

PROC SORT DATA = DFT;BY DUM;RUN;
PROC SORT DATA = LOGL1;BY DUM;RUN;
PROC SORT DATA = LOGL2;BY DUM;RUN;

DATA LOGL;
  MERGE LOGL1 LOGL2 DFT;
  BY DUM;
  CHI=NEG2LOGLRREDUCED - NEG2LOGLFULL;
  DF=FULL-REDUCED;
  PDOSEREPONSE=PUT(1-CDF('CHISQUARE',CHI,DF),PVALUE6.4);
RUN;

PROC PRINT DATA = LOGL;
TITLE 'PRIMARY ANALYSIS DOSE RESPONSE UNION INTERSECTION P-VALUE';
RUN;
TITLE;
QUIT;
```

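### The SAP gives the primary endpoint two unlinked decision rules, a 6-df test at 10% and a dose sequence at 2-sided 5%, and does not name the statistic of the second

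*SAP*

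**What the plan says.** **Rule 1, SAP 13.3.2 and 13.3.3.** The random-coefficients model is fitted with and without the treatment-by-time and treatment-by-time-squared terms. The change in −2 log likelihood is referred to chi-square on 6 df, and "this will provide the p-value to determine if the union intersection hypothesis can be rejected at the 10% alpha level". The next clause treats rejection, with no further step, as evidence that tildacerfont has an effect over placebo. This is labelled primary twice: "The dose response Primary Efficacy Analysis therefore corresponds to the formal hypothesis statement" in 13.3.2, and the Appendix D output title "PRIMARY ANALYSIS DOSE RESPONSE UNION INTERSECTION P-VALUE".

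**Rule 2, SAP 10.5.** "To control family-wise error rate, statistical hypothesis testing for the primary endpoint will be hierarchically dose ordered". The order is 200 mg, then 100 mg, then 50 mg, each against placebo at 2-sided 0.05 and each only if the dose before it succeeded. No model, parameter, time point or statistic is given. The section adds: "Secondary and exploratory endpoints will not be subject to alpha control".

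**Where dose-versus-placebo p-values are specified.** The first secondary analysis (13.4.1) takes from the primary model "the difference and associated 95% CI and p-value between each tildacerfont dose and placebo at each of 4, 8 and 12 weeks". Its supportive MMRM (13.4.1.1) says "the treatment effect for each tildacerfont dose versus placebo, being the corresponding difference in log scale LS means, will also be extracted", with p-values. The Appendix E code computes them for the second secondary analysis. SAP 13.3.5.1 applies the 13.3.3 methods to imputed data and reports a treatment effect, a 95% CI and a 2-sided p-value, without saying which test the p-value belongs to.

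**Alpha elsewhere.** SAP 9.2 defaults to 2-sided 0.05 unless otherwise noted. Protocol 9.4.1 sets 2-sided 0.05 for all efficacy analyses, and Protocol 9.6 leaves the multiplicity algorithm to the SAP. SAP Section 15 does not list the 10% level as a change.

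**The concern.** Both rules claim the primary endpoint, at different levels, and no sentence says whether the 6-df test opens the dose sequence, replaces it, or is enough alone. SAP Section 4 puts the SAP above the protocol, so it cannot settle a conflict inside the SAP. A team following the plan exactly could report a positive primary result by one section and a negative one by the other, and would be choosing between them after seeing the data.

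The rules also ask different questions. The 6-df test asks whether the arms' time profiles differ in shape after the first weeks. The dose sequence, on its most natural reading, asks whether each dose differs from placebo at Week 18. The quantity best suited to the sequence is specified under secondary analyses, which 10.5 itself leaves without alpha control.

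**Working it through.** **1. The plan's own figures.** Degrees of freedom: 3 doses × 2 interaction terms = 6, as stated. Chi-square(6) critical values are 10.64 at 10% and 12.59 at 5%. Sample size (SAP Section 7): 15 / 0.85 = 17.6, so 18 per arm, and 4 × 18 = 72, as stated. It rests on a difference of 50 with SD 30 between one dose and placebo, a standardised effect of 50/30 = 1.67. It is a pairwise calculation and gives no power for the 6-df test.

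**2. Type I error under each reading.** The 10.5 statistic is taken as the Week 18 contrast. Simulated figures use 200,000 runs and 18 per arm.

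| Reading | Null error |
|---|---|
| Dose sequence alone | at most 5% |
| 6-df test alone | 10% |
| Either suffices | bound 10% + 5% = 15%; if independent, 1 − 0.90 × 0.95 = 14.5%; simulated about 14% |
| 10% 6-df gate, then the sequence | about 0.7% to 1.2% (global null) |

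The two tests gave opposite answers in about 13% of simulated null trials.

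**3. What the 6-df test can see.** Treatment main effects stay in the reduced model (Appendix D code), so only between-visit changes that differ by arm count. With visits at 4, 8 and 12 weeks of treatment, compound symmetry, known covariance and all three doses reaching Δ at 12 weeks by linear growth, the noncentrality is

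NCP = (n/6) × Δ² / [σ²(1 − ρ)].

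Assumed, because the documents give no log-scale SD or correlation: Δ = ln 0.5 = −0.693, σ = 0.7, ρ from 0.3 to 0.8. For n = 18 and ρ = 0.3: NCP = 3 × 0.4805 / (0.49 × 0.7) = 4.20. For ρ = 0.8: 3 × 0.4805 / (0.49 × 0.2) = 14.71.

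| ρ | 0.3 | 0.5 | 0.7 | 0.8 |
|---|---|---|---|---|
| 6-df power at 10%, n = 18 | 40% | 52% | 75% | 90% |
| 6-df power at 5%, n = 18 | 28% | 40% | 63% | 83% |

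With n = 15 the range at 10% is 35% to 84%. With n = 18 it is 67% to above 99% for σ = 0.5 and 28% to 70% for σ = 0.9. With the plan's standardised effect of 1.67 and n = 18 it is 83% to above 99%. If the effect is constant from 4 to 12 weeks, NCP = 0 and the test rejects at about its alpha.

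**4. The 200 mg Week 18 contrast at 2-sided 5%.** z = 0.693 / (0.7 × √(2/18)) = 2.97, power 84%. With n = 15: z = 0.693 / (0.7 × √(2/15)) = 2.71, power 77%.

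**5. The contrast behind a 6-df gate** (n = 18, σ = 0.7, linear growth, ρ from 0.3 to 0.8): 37% to 77% with a 10% gate, 26% to 72% with a 5% gate.

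**The case against.** Several points on the other side stand.

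- **The 10.5 statistic is not wide open.** Table 1 of the SAP places the primary assessment at Week 18, the subgroup section (13.3.5.3) plots Week 18 effects by dose from the primary analysis, and Appendix E refers to the Week 18 treatment effect from the primary model. A reader might infer that a per-dose test of the whole profile is equally likely, but no passage describes one. What is missing is the formal assignment and its alpha status.
- **Inflation is not shown.** A reader might infer that the trial runs at 14% error. That needs a rule under which either test suffices, which the SAP neither states nor excludes. The serial reading is as plausible and gives about 1% under the global null.
- **A 10% level is not improper in itself.** SAP 9.2 allows another level if noted, 13.3.3 notes it, and a 10% screen for dose response is defensible in a Phase IIb dose-ranging study. Its absence from Section 15 is a documentation gap.
- **The 6-df test is not blind to the expected effect.** Protocol 2.3.2 and 4.2 describe a response that strengthens over 12 weeks, so the constant effect is a limiting case. With the plan's own standardised effect the 6-df test is well powered.
- **The power figures are assumption-driven.** Equal effects at all doses, compound symmetry and known covariance are simplifications. Effects graded 1 : 0.67 : 0.33 give 32% to 79% instead of 40% to 90%. A maximum-likelihood test against chi-square at 18 per arm rejected in about 12% and 6% of simulated trials at nominal 10% and 5%, so the nominal levels are approximate.

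None of this supplies the missing link between the two sections.

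**Conclusion.** The point holds without any assumption: there are two rules for one primary endpoint, at 10% and 5%, with no statement of how they combine and no named statistic for the second. Until that is settled, the primary Type I error can be put anywhere from about 1% (under the global null) to about 14%, depending on the reading.

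The consequence for power rests on the assumed SD, correlation and growth pattern. At log SD 0.7 the choice of rule moves power between 84% for the 200 mg contrast alone, 40% to 90% for the 6-df test at 10%, and 37% to 77% for the contrast behind a 10% gate. With a larger standardised effect the loss in the 6-df test is much smaller. The documents do not support saying that error is inflated, that the sequence has no candidate statistic, or that the 6-df test will miss the expected effect. The ambiguity should be resolved before unblinding.

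**What to change.** Before unblinding:

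1. State in both SAP 10.5 and 13.3.3 which test decides the primary endpoint, and whether the 6-df test gates the dose sequence or is supportive. If it gates, note that its null is not the intersection of the Week 18 dose nulls.
2. Name the 10.5 statistic. The Week 18 dose-versus-placebo contrast from the 13.3.3 model is the reading the documents best support. Give it one alpha status, so that it is not both primary under 10.5 and uncontrolled under 13.4.1. Say which test the p-value in 13.3.5.1 refers to.
3. Hold the deciding rule to the 2-sided 0.05 of 10.5 and Protocol 9.4.1, or label the 10% test a non-confirmatory screen and remove its stand-alone conclusion. If 10% is kept as the deciding level, record it in Section 15 and drop the 5% family-wise claim.
4. If the dose sequence decides, align the dose-response primary wording in Protocol 3 and 9.4.2. If the 6-df test decides, state that it cannot detect an effect constant from 4 to 12 weeks.

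Cost: one test loses stand-alone confirmatory status, and which one is the sponsor's choice. If the dose sequence decides, a protocol alignment is needed, and no lower dose can be claimed if 200 mg fails, as 10.5 already implies. If the 6-df test decides at 5%, its power falls from 40% to 28% at correlation 0.3 and from 90% to 83% at 0.8 (log SD 0.7, 18 per arm). No new data are needed.
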